10.3 Financial Disclosure and Obligations

Investigators and sub-investigators are required to provide financial disclosure information to allow the sponsor to submit the complete and accurate certification or disclosure statements required under 21 CFR 54. In addition, the investigator must provide to the sponsor a commitment to promptly update this information if any relevant changes occur during the course of the investigation and for 1 year following completion of the study.

Neither the sponsor nor PPD is financially responsible for further testing or treatment of any medical condition that may be detected during the screening process. In addition, in the absence of specific arrangements, neither the sponsor nor PPD is financially responsible for further treatment of the participant's disease.

10.4 Investigator Documentation

Before beginning the study, the investigator will be asked to comply with ICH E6(R2) Section 8.2 and Title 21 of the CFR by providing all essential documents, including but not limited to the following:

- IRB approval.
- Original investigator-signed agreement page of the protocol.
- Curriculum vitae for the investigator and each sub-investigator.
- Financial disclosure information to allow the sponsor to submit complete and accurate certification or disclosure statements required under 21 CFR 54. In addition, investigators must provide to the sponsor a commitment to promptly update this information if any relevant changes occur during the course of the investigation and for 1 year after the completion of the study.
- IRB-approved informed consent, samples of site advertisements for recruitment for this study, and any other written information regarding this study that is to be provided to the participant.
- Signed Clinical Study Agreement.

10.5 Study Conduct

The investigator agrees that the study will be conducted according to the principles of ICH E6(R2) and all applicable guidelines and regulations. The investigator will conduct all aspects of this study in accordance with all national, state, and local laws or regulations. Study information from this protocol will be posted on publicly available clinical study registers before enrollment of participants begins.

10.6 Adverse Events and Study Report Requirements

The investigator agrees to submit reports of SAEs to the sponsor and/or the IRB according to the timeline and method outlined in the protocol. In addition, the investigator agrees to submit annual reports to the study site IRB as appropriate.

10.7 Investigator's Final Report

Upon completion of the study, the investigator, where applicable, should inform the institution; the investigator/institution should provide the IRB with a summary of the study's outcome and the sponsor and regulatory authority(ies) with any reports required.

11 Study Management

11.1 Monitoring

11.1.1 External Data Monitoring Committee

No data monitoring committee is planned for this study.

11.1.2 Monitoring of the Study

The clinical monitor, as a representative of the sponsor, has the obligation to follow the study closely. In doing so, the monitor will visit the investigator and study site at periodic intervals, in addition to maintaining necessary phone and letter contact. The monitor will maintain current personal knowledge of the study through observation, review of study records and source documentation, and discussion of the conduct of the study with the investigator and personnel.

The medical monitor and sponsor will hold monthly meetings to review AEs noted during the month, unless an SAE is noted and reported as described in Section 6.3.5.5.

All aspects of the study will be carefully monitored, by the sponsor or its designee, for compliance with applicable government regulation with respect to current GCP and current standard operating procedures.

11.1.3 Inspection of Records

Investigators and institutions involved in the study will permit study-related monitoring, audits, IRB review, and regulatory inspections by providing direct access to all study records. In the event of an audit, the investigator agrees to allow the sponsor, representatives of the sponsor, or a regulatory agency access to all study records.

The investigator should promptly notify the sponsor and PPD of any audits scheduled by any regulatory authorities and promptly forward copies of any audit reports received to the sponsor.

11.2 Management of Protocol Amendments and Deviations

11.2.1 Modification of the Protocol

Any changes in this research activity, except those necessary to remove an apparent immediate hazard to the participants, must be reviewed and approved by the sponsor or its designee. Amendments to the protocol must be submitted in writing to the investigator's IRB for approval before participants can be enrolled into an amended protocol.

11.2.2 Protocol Deviations

The investigator or designee must document and explain in the participant's source documentation any deviation from the approved protocol. The investigator may implement a deviation from, or a change of, the protocol to eliminate an immediate hazard to study participants without prior IRB approval. As soon as possible after such an occurrence, the implemented deviation or change, the reasons for it, and any proposed protocol amendments should be submitted to the IRB for review and approval, to the sponsor for agreement, and to the regulatory authorities, if required.

A deviation from the protocol is an unintended or unanticipated departure from the procedures or processes approved by the sponsor and the IRB and agreed to by the investigator. A significant deviation occurs when there is nonadherence to the protocol by the participant or investigator that results in a significant additional risk to the participant. Significant deviations can include nonadherence to inclusion or exclusion criteria, enrollment of the participant without prior sponsor approval, or nonadherence to FDA regulations or ICH GCP guidelines and will lead to the participant being withdrawn from the study (Section 4.4).

Protocol deviations will be documented by the clinical monitor throughout the course of monitoring visits. Principal investigators will be notified in writing by the monitor of deviations. The IRB should be notified of all protocol deviations in a timely manner.

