4.4 Discontinuation From Study Treatment and/or Withdrawal From the Study

4.4.1 Discontinuation From Study Treatment

4.4.1.1 Permanent Discontinuation

All efforts should be made to keep participants on treatment.

In rare instances, it may be necessary for a participant to permanently discontinue study treatment. Before permanent discontinuation of treatment regardless of the reason or as soon as possible after the decision for discontinuation has been made, if possible, the participant will undergo all procedures planned for the last dosing day with Soliqua 100/33 and the follow-up visit (Section 13.1).

All cases of permanent treatment discontinuation (Section 4.4.3) must be recorded by the investigator in the appropriate pages of the electronic case report form (eCRF) when confirmed.

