4.4.3 Handling of Withdrawals

Participants are free to withdraw from the study or study treatment at any time upon request. Their participation in the study may be stopped at any time at the discretion of the investigator or at the request of the sponsor.

If the participant withdraws consent for disclosure of future information, the sponsor may retain and continue to use any data collected before such a withdrawal of consent.

If a participant withdraws from the study, they may request destruction of any samples taken and not tested, and the investigator must document this in the site study records.

Participants who discontinue study treatment or active participation in the study will no longer receive study drug. When a participant withdraws from the study, the reason(s) for withdrawal shall be recorded by the investigator on the relevant page of the eCRF.

A participant may withdraw from the study or study treatment under the circumstances (including, but not limited to) listed below:

- The participant intends to become pregnant.
- The participant may be withdrawn at the discretion of the investigator due to noncompliance or due to a safety concern.
- The participant will be withdrawn if starting any drugs that interfere with glucose metabolism (eg, steroid doses equivalent to prednisone ≥5 mg/day).
- The participant may be withdrawn if diagnosed with acute pancreatitis (defined as meeting 2 of the following 3 rules: typical abdominal pain; amylase/lipase >3 × ULN; and/or characteristic ultrasound, computed tomography, or magnetic resonance imaging findings).
- If the fasting or the mean SMPG value during 3 consecutive days is >300 mg/dL, the investigator will schedule an unplanned visit as soon as possible to obtain confirmatory FPG and investigate the cause. If no apparent or intercurrent cause is detected, the participant may be withdrawn.
- The participant has recurrent severe hypoglycemia or recurrent nocturnal hypoglycemia during the treatment period that poses a potential risk to the participant, as judged by the investigator.
- The participant is unable to comply with the study protocol, at the investigator's discretion.

Whenever possible, all participants who discontinue study treatment or withdraw from the study prematurely will undergo all end-of-study and follow-up assessments. Participants who fail to return for final assessments will be contacted by the site in an attempt to have them comply with the protocol.

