
CGM data will require device reinsertion. Eligibility and analysis criteria for CGM measures are provided in Section 13.9.

No. of Days CGM Device Worn ^a	Time CGM Device Active (%) ^a	Equivalent Days
8	100	8.00
9	89	8.01
10	80	8.00
11	73	8.01
12	67	8.04
13	62	8.01
14	57	7.98

Table 6-1Criteria for CGM Device Reinsertion

Abbreviations: AGP, Ambulatory Glucose Profile; CGM, continuous glucose monitoring. ^a AGP report.

Figure 6–1 Criteria for CGM Device Reinsertion

Abbreviation: CGM, continuous glucose monitoring.

Participants with less than equivalent of 8 days of evaluable CGM data (not necessarily consecutive) of a 14-day period (eg, days of CGM device wear \times % time CGM device active < 8) during the run-in period will be considered as screen failures. For participants

Sanofi	SOLIQUA TM 100/33
Protocol: LPS16990 (Original, Version 1.0)	18 Aug 2021

who discontinue study treatment prematurely, the visit window can be extended by 14 days to collect the CGM data before they permanently discontinue the treatment.

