eDiary completion	<					X					>
Daily IMP dosing ^t				<		>	X		>		
IMP dose adjustments					X	Х	Х			Х	
Concomitant medications			х	X	x	х	х	х	Х	х	Х
IMP adherence assessment						х		Х	х		
FPG ^v			Х					-	Х		
DM-SAT ^w			X					-	X		

Sanofi Protocol: LPS16990 (Original, Version 1.0)

Run-in			i-in	Treatment ^a							
Study Period	Screening			Baseline		Titration ^t	•				
Visit ^c	1	2	3.1 ^d	3.2 ^{e,f}	4.0-4.6 ^g	5	5.1-5.4 ^h	6	7 ⁱ	Unscheduled ^j	8
Visit Type	Clinic	Clinic or Home	Clinic	Phone ^e	Phone	Clinic or Home	Phone	Clinic or Home	Clinic	Clinic or Home	Phone
Week	-4	-2	0	0	1 to 7	8	9 to 12	14	16		18
Day	-28	-15 ^k	-1	0	1 to 49	56	63 to 84	98	112		126
Window (Days)				7 ^{(±2)e}		±3		±3	±3		±3
Hypoglycemia events ^x	х	х	х	Х	х	х	х	х	х	х	х
Recording of AEs/SAEs (including AESIs)	x	х	х	х	х	х	х	Х	х	х	х
Product complaints					Х	Х	Х	Х	Х		
Vital signs (including heart rate, systolic and diastolic BP)	х		х						х		
Calcitonin	Х										
Clinical chemistry	Х		Х						Х		
Hematology	Х		Х						Х		
Urinalysis ^y	Х		Х						Х		
Pregnancy test ^z	Х		Х			Х			х		

Abbreviations: ADA, American Diabetes Association; AE, adverse event; AESI, adverse event of special interest; BMI, body mass index; BP, blood pressure; CGM, continuous glucose monitoring; DM-SAT, Diabetes Medications Satisfaction Questionnaire; DPP-4i, dipeptidyl peptidase-4 inhibitor;

DTP, direct-to-patient; eDiary, electronic diary; FPG, fasting plasma glucose; GLP-1 RA, glucagon-like peptide-1 receptor agonist; Hb, hemoglobin;

HbA1c, glycated hemoglobin; HCP, healthcare provider; IMP, investigational medicinal product; MMTT, mixed-meal tolerance test; OAD, oral antidiabetic drug; PPG, postprandial glucose; SAE, serious adverse event; SMPG, self-measured plasma glucose; SU, sulfonylurea.

^a For participants who discontinue study treatment prematurely, the visit window can be extended by 14 days to collect the CGM data, followed by MMTT data, before they permanently discontinue the treatment. Before permanent discontinuation of treatment regardless of the reason or as soon as possible after the decision for discontinuation has been made, if possible, the participant will undergo all procedures planned for the last dosing day with Soliqua 100/33 and the follow-up visit (ie, Visit 7 and above).

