4.3 PRIMARY ENDPOINT(S) ANALYSIS

4.3.1 Definition of endpoint(s)

The primary endpoint is the difference from baseline to week 16 in the percentage of TIR of 70-180 mg/dL using 14 days of CGM data at baseline. The percentage of time spent in the glycemic target range will be calculated as 100 times the number of recorded measurements in the glycemic target range, (70-180 mg/dL) inclusive, divided by the total number of recorded measurements. All the efficacy assessments collected during the study will be used, including those obtained after IMP discontinuation or introduction of rescue therapy. Regardless of intercurrent events at week 16, the value for the mean change in the percentage of TIR will be used.

CGM data

CGM compliance is defined as:

1. at least 8 out of 14 days (not necessarily consecutive) have 100% of evaluable CGM data per 24-hour period (total of 768 records on 8 days) OR
2. at least 9 out of 14 days (not necessarily consecutive) have $\geq 89\%$ of evaluable CGM data per 24-hour period (total of 768 records on 9 days and at least 9 days with 85 records minimum) OR
3. at least 10 out of 14 days (not necessarily consecutive) have at least $\geq 80\%$ of evaluable CGM data per 24-hour period (total of 768 records on 10 days and at least 10 days with 77 records minimum)

during baseline (the run-in period) as well as week 16.

During the run-in period or end of treatment period, CGM device reinsertion will be allowed for participants who do not meet the compliance criteria over a 14-day period as a result of premature sensor failure.

Baseline will be defined as the first 14 evaluable days of evaluable CGM data prior to first day of treatment and referred to as the run-in period in the graphical study design. An evaluable day is defined as a 24-hour period with $\geq 80\%$ non-missing measurements. Only evaluable days will be included in the analysis. Week 16 will be defined as the first 14 evaluable days of evaluable CGM data starting at day 95 or later.

The first day of CGM data will start at time of device insertion and subsequent days will start every 24 hours. If the device is re-inserted, device with the most compliant data will be used and if neither session is evaluable, the combined data from both sessions will be used as evaluable data. For subsequent reinsertions, the day will start at time of reinsertion.

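### Automatic study withdrawal for significant deviations (Protocol 11.2.2) causes avoidable loss of Week 16 CGM, and the SAP is inconsistent on how that loss is handled

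*Protocol*

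**What the plan says.** **The deviation rule.** Protocol 11.2.2 defines a significant deviation as "nonadherence to the protocol by the participant or investigator that results in a significant additional risk to the participant". Its examples include breaches of eligibility criteria, enrolment without sponsor approval and departures from FDA regulations or GCP. The stated consequence is fixed: "guidelines and will lead to the participant being withdrawn from the study (Section 4.4".

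**The section it cites.** Section 4.4.3 uses discretionary wording: "The participant may be withdrawn at the discretion of the investigator due to noncompliance or due to a safety concern". It also asks for data from leavers: "Whenever possible, all participants who discontinue study treatment or withdraw from the study prematurely will undergo all end-of-study and follow-up assessments". That sentence gives no timing.

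**Collection after stopping drug.** Three places tie collection to the time of exit:
- Section 4.4.1.1 says that, before or as soon as possible after the decision to stop, "the participant will undergo all procedures planned for the last dosing day with Soliqua 100/33 and the follow-up visit (Section 13.1".
- Section 6.2.1 allows a 14-day extension "to collect the CGM data before they permanently discontinue the treatment".
- Schedule of Events footnote a says "the visit window can be extended by 14 days to collect the CGM data, followed by MMTT data, before they permanently discontinue the treatment".

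**Estimand and analysis.** Protocol 8.1 places both drug discontinuation and study withdrawal under treatment policy, with an ITT aim. The footnote to SAP Table 3 lists only rescue medication and drug discontinuation. SAP 4.3.1 accepts assessments made after drug is stopped, but fixes the window: "Week 16 will be defined as the first 14 evaluable days of evaluable CGM data starting at day 95 or later". SAP 4.3.2 carries the baseline value forward for all missing Week 16 data not due to CGM technical problems, so the change is 0. SAP Table 3 computes the primary mean for participants who are CGM-compliant at both baseline and Week 16.

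**The concern.** A treatment-policy estimand needs the Week 16 measurement whatever happened to treatment. The SAP is ready to use off-drug data, but the deviation rule removes people from the study before such data can be collected. The added risk that defines a significant deviation may justify stopping the drug. It does not by itself justify stopping a blinded sensor worn for two weeks. The rule also covers breaches by the investigator, where the participant has done nothing that calls for leaving.

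At stake are a small number of primary endpoint values that could have been measured. They would be replaced by an assumption of no change, or dropped, depending on which part of the SAP is followed.

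**Working it through.** **1. Route from deviation to missing value.** Visit 6 is on day 98 with a window of 3 days, so the earliest planned sensor placement is day 98 − 3 = 95, which matches the SAP window. Someone whose participation ends before day 95 has no Week 16 CGM. The 14-day extension helps only those whose exit is already close to day 95. SAP 4.3.2 and Table 3 then point to different treatments, so both are worked below.

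**2. The plan's own figure.** Inputs from Protocol 8.3 and SAP section 2: mean change 10, SD 25, two-sided 0.05, 95% power, 82 evaluable, 100 enrolled, 15% loss.
- n = [25 × (1.960 + 1.645) / 10]² = 81.2, rounded up to 82. This reproduces.
- Power at 82 is 95.2% by the normal formula and 94.7% by the noncentral t.
- 82 / 0.85 = 96.5, or 97 participants; the plan rounds up to 100.

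**3. Carry-forward reading (SAP 4.3.2).** Take N = 100 treated, of whom k are withdrawn under 11.2.2 before day 95 although they could have stayed on drug. The documents give no rate, so k is assumed. With p = k/100:
- mean = 10(1 − p)
- variance = (1 − p) × 625 + p(1 − p) × 100
- power from the two-sided one-sample t-test (noncentral t, N = 100)

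| Zero-scored | Mean | SD | Power |
|---|---|---|---|
| 0 | 10.0 | 25.00 | 97.7% |
| 2 | 9.8 | 24.79 | 97.5% |
| 3 | 9.7 | 24.68 | 97.3% |
| 5 | 9.5 | 24.46 | 97.0% |
| 15 | 8.5 | 23.32 | 95.0% |
| 17 | 8.3 | 23.08 | 94.5% |
| 20 | 8.0 | 22.72 | 93.7% |

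Each zero in place of the planned change lowers the mean by 10/100 = 0.1 TIR point. If the unseen change lies between 0 and 10, the shift is between 0 and 0.1.

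**4. Exclusion reading (SAP Table 3).** The mean is not shifted mechanically; any bias depends on how leavers differ from the rest. Only n falls, with mean 10 and SD 25 unchanged. Power is 97.7% at n = 100, 97.5% at n = 98 and 97.1% at n = 95.

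**5. Share due to the rule itself.** Suppose 5 are withdrawn but 3 of them had to stop drug for safety and would have been lost anyway under exit-time collection. The rule then accounts for the step from 3 to 5 zeros: mean 9.7 to 9.5, power 97.3% to 97.0%.

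**6. On top of planned losses.** If the planned 15 discontinuations are also zero-scored, power starts at 95.0% and goes to 94.5% (k = 2, 17 zeros) or 93.7% (k = 5, 20 zeros).

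**The case against.** **The two sections can coexist.** Section 11.2.2 covers a narrow, higher-risk class. The list in 4.4.3 is expressly not exhaustive, already contains one mandatory item (starting drugs that interfere with glucose metabolism), and allows participation to be stopped at the sponsor's request. This stands. A reader might infer a flat contradiction, but the text supports only a tension: 11.2.2 cites Section 4.4 without reconciling its fixed consequence with the discretion there.

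**The affected group may be very small.** Significant added risk is part of the definition, so many of these participants would come off drug anyway, and exit-time collection would lose them whatever 11.2.2 says. This stands, and step 5 separates them out.

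**Follow-up is already requested.** Section 4.4.3 asks for end-of-study assessments from all leavers where possible. A reader might infer that it permits collection only at exit. It does not say so; the exit timing comes from 4.4.1.1, 6.2.1 and footnote a.

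**Any withdrawal rule strains a treatment-policy estimand, and the SAP's list of intercurrent events omits study withdrawal.** Both are true. What is particular to 11.2.2 is that withdrawal is automatic even where nobody has judged it necessary.

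**Zero-scoring.** A reader of SAP 4.3.2 alone might infer that every early leaver is scored as no change. SAP Table 3 points to exclusion, so this is not settled.

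**Conclusion.** The point holds as a minor one. The automatic wording in 11.2.2 produces avoidable missing Week 16 CGM, against the aim in Protocol 8.1, and the SAP does not say consistently whether such participants count as zero change or are left out.

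With 5 of 100 affected and no other losses, power falls by 0.7 percentage points under carry-forward (97.7% to 97.0%) or 0.6 under exclusion (97.7% to 97.1%). These figures rest on the planned change of 10 and SD of 25, 100 treated participants, and an assumed number of withdrawals. Under carry-forward the bias is toward no effect if the unseen changes are positive.

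The two sensitivity analyses in SAP 4.3.3, one carrying baseline forward for all missing Week 16 data and one excluding missing data, bracket the result if the unseen change lies between zero and the mean of the others. They cannot supply the uncollected values. A reader might infer that the primary conclusion is at risk; the figures do not support that.

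A reader might also infer that treated participants later found ineligible drop out of the efficacy set, because the enrolled set is worded in terms of eligible participants. SAP 4.2 ties enrolment to dispensing, 5.4.5 places it at the first-dose visit, and 5.3.1 summarises deviations within the enrolled set. These point the other way.

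**What to change.** 1. **Protocol 11.2.2:** state that a significant deviation leads to stopping study drug where safety requires it, but does not by itself end study participation.
2. **Protocol 4.4.1.1, 6.2.1 and Schedule of Events footnote a:** add that consenting participants off drug still have the scheduled Week 14 to 16 CGM and Visit 7. Align the same exit-time sentence where it recurs (6.2.2, 13.9, the synopsis and the SAP copy of footnote a).
3. **Protocol 4.4.3:** the request for end-of-study assessments is already there; add only when they take place.
4. **SAP Table 3 and 4.3.2:** make them agree on whether a participant with no Week 16 CGM for non-technical reasons is imputed or excluded.

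The cost is a sentence in each place. Off-drug participants keep a few visits that are already planned, and data from participants with deviations stay in the main analysis, as a treatment-policy estimand intends. The safety purpose of 11.2.2 is kept, because drug is still stopped where needed.
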